##### Safety QTcF Assessment

Degree of Prolongation	Mild (ms)	Moderate (ms)	Severe (ms)
Absolute value	>450-480	>480-500	>500
Increase from baseline		30-60	>60

#### 9.4.6. Other Analyses

Pharmacogenomic or biomarker data from Retained Research Samples may be collected during or after the trial and retained for future analyses; the results of such analyses are not planned to be included in the CSR.

#### 9.5. Interim Analyses

No formal interim analysis will be conducted for this study. As this is an open-label study, the sponsor may conduct unblinded reviews of the data during the course of the study for the purpose of safety assessment, and/or supporting clinical development.

#### 9.6. Sample Size Determination

Phase 2 of the study will not be initiated per business decision made by Pfizer (protocol amendment 2).

**Phase 1b:**

The primary objective in the Phase 1b of the study is to assess DLTs, safety and tolerability of PF-07901801 in combination with tafasitamab and lenalidomide in order to select up to 2 fixed doses of PF-07901801 to explore in Phase 2. The target number of participants per cohort is 2-4, and a minimum of 2-4 DLT-evaluable participants is required at each tested dose level of PF-07901801. Approximately 6 to 9 DLT-evaluable participants will be treated at the MTD or highest safe tested dose level for PF-07901801 before proceeding to Phase 2. The actual number of participants to be enrolled will depend on the number of dose levels evaluated and the number of participants treated at each dose level. It is estimated that approximately 20 participants will be enrolled in Phase 1b.

If any participant is deemed non-evaluable for DLT, additional participants may be enrolled to ensure there are a sufficient number of evaluable participants in the Phase 1b.

**Phase 2:**

Up to 2 fixed doses will be selected based on Phase 1b data for further evaluation in Phase 2 of the study. Approximately 25 participants will be treated for each selected dose. The sample size is not determined based on statistical hypothesis testing considerations; rather, it is based on clinical considerations that the stated sample size will provide sufficient evidence of preliminary antitumor activity of PF-07901801 in combination with tafasitamab and lenalidomide, and for dose selection based on exposure-response analyses.

ORR can be estimated with a maximum standard error of 10% with 25 participants per arm.

[Table 11](#) provides the 95% CIs for ORR based on Wilson method for different observed responses.

**Table 11. Sample Size and 95% CI for ORR based on Wilson Method (with Continuity Correction)**

N = 25	Number of responses	Observed ORR	95% CI for ORR
1	0.04	0.002, 0.223	
2	0.08	0.014, 0.275	
3	0.12	0.032, 0.323	
4	0.16	0.053, 0.369	
5	0.2	0.076, 0.413	
6	0.24	0.102, 0.455	
7	0.28	0.129, 0.496	
8	0.32	0.157, 0.536	
9	0.36	0.187, 0.574	
10	0.4	0.218, 0.611	
11	0.44	0.250, 0.647	
12	0.48	0.283, 0.682	
13	0.52	0.318, 0.717	
14	0.56	0.353, 0.750	
15	0.6	0.389, 0.782	
16	0.64	0.426, 0.813	
18	0.72	0.504, 0.871	
20	0.8	0.587, 0.924	
22	0.88	0.677, 0.968	

### 9.7. Statistical Methods and Decision Criteria

The mTPI-2 design (with target  $pT=0.3$ ,  $e1=0.05$ ,  $e2=0.05$ ) will be utilized for dose finding of the combination therapy, with the dose level of tafasitamab and lenalidomide fixed. The mTPI-2 design uses a Bayesian statistics framework and a beta binomial hierarchical model to compute the UPM of dosing intervals. The dose interval that has the largest UPM is selected as the winning model. The dose de-escalation/escalation recommendation is as shown below:

- If intervals  $\{(0.15, 0.25), (0.05, 0.15), (0, 0.05)\}$  exhibit the largest UPM: escalate to next higher dose;
- If interval  $(0.25, 0.35)$  exhibits the largest UPM: stay at current dose;
- If intervals  $\{(0.35, 0.45), (0.45, 0.55), (0.55, 0.65), (0.65, 0.75), (0.75, 0.85), (0.85, 0.95), (0.95, 1)\}$  exhibit the largest UPM: de-escalate to a lower dose.

The decision rules for mTPI-2 design (target  $pT=0.3$ ,  $e1=0.05$ ,  $e2=0.05$ ) are listed in [Table 12](#).

**Table 12. mTPI-2 Decision Rules (pT=0.3, e1=0.05, e2=0.05)**

Number of Patients with DLTs	Number of Patients														
	1	2	3	4	5	6	7	8	9	10	11	12	13	14	15
0	E	E	E	E	E	E	E	E	E	E	E	E	E	E	E
1	D	D	S	S	E	E	E	E	E	E	E	E	E	E	E
2		DU	D	D	D	S	S	S	E	E	E	E	E	E	E
3			DU	DU	D	D	D	D	S	S	S	S	E	E	E
4				DU	DU	DU	D	D	D	D	D	S	S	S	S
5					DU	DU	DU	DU	DU	D	D	D	D	D	S
6						DU	DU	DU	DU	DU	D	D	D	D	D
7							DU	D	D						
8								DU							
9									DU						
10										DU	DU	DU	DU	DU	DU
11											DU	DU	DU	DU	DU
12												DU	DU	DU	DU
13													DU	DU	DU
14														DU	DU
15															DU

E = Escalate to the next higher dose level

S = Stay at the current dose level

D = De-escalate to the next lower dose level

DU = The current dose level is unacceptably toxic and should be eliminated from further dose finding

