2.1. Modifications to the Analysis Plan Described in the Protocol

[figure not shown]
Not applicable.

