5.1.2. Decision Rules

Phase 1b

The mTPI-2 design (with target pT=0.3, e1=0.05, e2=0.05) will be utilized to estimate the MTD of PF-07901801, in combination with standard doses of tafasitamab and lenalidomide. Other evidence such as safety data beyond DLT window, clinical activity, PK, PD and biomarker data will also be evaluated in determining the recommended doses for further development in the Phase 2.

The mTPI-2 design uses a Bayesian statistics framework and a beta binomial hierarchical model to compute the unit probability mass (UPM; the ratio of the probability mass of the interval to the length of the interval) of dosing intervals. The dose interval that has the largest UPM is selected as the winning model. The dose de-escalation/escalation recommendation for the mTPI-2 design with target $pT=0.3$, $e1=0.05$, $e2=0.05$ is as follows:

- If intervals $\{(0.15, 0.25), (0.05, 0.15), (0, 0.05)\}$ exhibit the largest UPM: escalate to next higher dose;
- If interval $(0.25, 0.35)$ exhibits the largest UPM: stay at current dose;
- If intervals $\{(0.35, 0.45), (0.45, 0.55), (0.55, 0.65), (0.65, 0.75), (0.75, 0.85), (0.85, 0.95), (0.95, 1)\}$ exhibit the largest UPM: de-escalate to next lower dose.

The detailed decision rules for mTPI-2 design with target $pT=0.3$, $e1=0.05$, $e2=0.05$ are listed in [Table 3](#).

Table 3 mTPI-2 Decision Rules (pT=0.3, e1=0.05, e2=0.05)

Number of Patients with DLTs	Number of Patients														
	1	2	3	4	5	6	7	8	9	10	11	12	13	14	15
0	E	E	E	E	E	E	E	E	E	E	E	E	E	E	E
1	D	D	S	S	E	E	E	E	E	E	E	E	E	E	E
2		DU	D	D	D	S	S	S	E	E	E	E	E	E	E
3			DU	DU	D	D	D	D	S	S	S	S	E	E	E
4				DU	DU	DU	D	D	D	D	D	S	S	S	S
5					DU	DU	DU	DU	DU	D	D	D	D	D	S
6						DU	DU	DU	DU	DU	DU	D	D	D	D
7							DU	D	D						
8								DU							
9									DU						
10										DU	DU	DU	DU	DU	DU
11											DU	DU	DU	DU	DU
12												DU	DU	DU	DU
13													DU	DU	DU
14														DU	DU
15															DU

E = Escalate to the next higher dose level

S = Stay at the current dose level

D = De-escalate to the next lower dose level

DU = The current dose level is unacceptably toxic and should be eliminated from further dose finding

Phase 2

There are no formal decision rules for Phase 2.

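### At 6 DLTs in 11 patients, protocol Table 12 says de-escalate and SAP Table 3 says eliminate the dose; the protocol cell also conflicts with its own entry at 5 in 9 (minor)

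*Protocol*

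**What the plan says.** Protocol 9.7 describes a design that "uses a Bayesian statistics framework and a beta binomial hierarchical model to compute the UPM of dosing intervals". It lists eleven intervals for the DLT rate and attaches escalate, stay or de-escalate to whichever has the largest unit probability mass (UPM). For the seven intervals above 0.35 the instruction is that, if they "exhibit the largest UPM: de-escalate to a lower dose", the next cohort goes down. SAP 5.1.2 gives the same intervals and rules. Neither text gives a prior or a probability threshold for elimination.

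Elimination appears only in the tables (protocol Table 12, SAP Table 3), through the code DU: "DU = The current dose level is unacceptably toxic and should be eliminated from further dose finding".

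For 6 DLTs the rows run from n = 6 to n = 15:

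- Protocol Table 12: "6 DU DU DU DU DU D D D D D", so DU at n = 6–10 and D at n = 11–15.
- SAP Table 3: "6 DU DU DU DU DU DU D D D D", so DU at n = 6–11 and D at n = 12–15.

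For 5 DLTs, n = 5 to 15, both tables print "5 DU DU DU DU DU D D D D D S", so 5/9 is DU in both.

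SAP 2.1, headed "Modifications to the Analysis Plan Described in the Protocol", is marked not applicable. The SAP's own summary of changes and the protocol's amendment summaries name no change to the decision rules.

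**The concern.** Two tables for one design should agree in every cell, and here the text cannot say which is right. The largest-UPM rule gives de-escalation at 6/11, but it gives the same at every DU cell. What separates D from DU is an elimination threshold that neither document states.

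The protocol table also conflicts with itself. It discards a dose after 5 DLTs in 9 patients, yet leaves the dose available after 6 in 11, where the evidence of excess toxicity is stronger.

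The table is the pre-specified dose rule for the Phase 1b primary objective. D permits a return to the dose later and DU forbids it. The protocol governs conduct at the sites, and it carries the less protective entry.

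**Working it through.** **Inputs.** Target 0.3, e1 = e2 = 0.05, and the eleven intervals, from protocol 9.7. Printed decisions from protocol Table 12 and SAP Table 3. Assumed, because not stated: a Beta(1,1) prior, and DU when P(p > 0.3 | x, n) exceeds a cut-off c.

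**Cells compared.** Rows 0–6 (90 cells) and rows 10–15 (21 cells) are complete in both tables, 111 cells in all. Rows 7–9 are truncated in the text copy of both documents and were not used.

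**Formulas.** With x DLTs in n patients the posterior is Beta(1 + x, 1 + n − x). The UPM of an interval is its posterior probability divided by its length. Under this prior, P(p > 0.3 | x, n) = P(Bin(n + 1, 0.3) ≤ x).

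**Reproducing the tables.** With c = 0.95, the calculation matches the SAP in 111 of 111 cells and the protocol in 110 of 111. The only miss is 6/11: printed D, calculated DU. The largest UPM at 6/11 falls in (0.45, 0.55).

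**The two cells in conflict.**

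- 5/9: P(Bin(10, 0.3) ≤ 5) = 0.02825 + 0.12106 + 0.23347 + 0.26683 + 0.20012 + 0.10292 = 0.95265
- 6/11: P(Bin(12, 0.3) ≤ 6) = 0.01384 + 0.07118 + 0.16779 + 0.23970 + 0.23114 + 0.15850 + 0.07925 = 0.96140

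**What cut-off do the tables imply?**

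| Cell | P(p > 0.3) | Protocol | SAP |
|---|---|---|---|
| 5/10 | 0.9218 | D | D |
| 6/12 | 0.9376 | D | D |
| 4/7 | 0.9420 | D | D |
| 5/9 | 0.9527 | DU | DU |
| 6/11 | 0.9614 | **D** | **DU** |
| 3/4 | 0.9692 | DU | DU |
| 6/10 | 0.9784 | DU | DU |

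In the SAP the highest non-DU value is 0.9420 and the lowest DU value is 0.9527, so any cut-off from 0.9420 to just under 0.9527 reproduces it. In the protocol the highest non-DU value (0.9614) lies above the lowest DU value (0.9527), so no cut-off works.

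**Dependence on the prior.** Over a grid of Beta(a, b) priors with a from 0.05 to 3 and b from 0.05 to 7 in steps of 0.05 (60 × 140 = 8,400 pairs), P at 6/11 exceeded P at 5/9 every time.

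**How often the cell is reached.** All sequences of cohorts of 2–4 summing to 11 were enumerated, staying at the dose only after S. The most likely route uses cohorts of 4, 3 and 4 and passes through 1/4 (S) and 2/7 (S), then 4 DLTs in 4:

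- True rate 0.4: (4 × 0.4 × 0.6³) × (3 × 0.4 × 0.6²) × 0.4⁴ = 0.3456 × 0.432 × 0.0256 = 0.0038
- True rate 0.5: 0.25 × 0.375 × 0.0625 = 0.0059

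If E at the top dose also allows staying, the maximum comes from cohorts of 3, 4 and 4. The count at n = 7 must be 2, reached from 0/3 or 1/3:

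- True rate 0.4: (0.216 + 0.432) × 0.3456 × 0.0256 = 0.0057
- True rate 0.5: (0.125 + 0.375) × 0.28125 × 0.0625 = 0.0088, where 0.28125 = 0.75 × 0.375 reflects the branch structure: 0.125 × 0.375 + 0.375 × 0.25 = 0.140625, and 0.140625 × 0.0625 = 0.0088

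Routes that return to the dose after a D are not counted.

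**The case against.** **A reading error.** The discrepancy is one letter in one cell of a table taken from PDF, and rows 7–9 of the same table have visibly lost cells. A full count of ten entries rules out a dropped or shifted cell but not a misread one. This stands in part: the cell must be confirmed on the source PDF. It is not decisive. The losses in rows 7–9 are the same in both documents and fit the collapse of long runs of DU entries, which would not touch row 6, and the other 110 cells compared agree.

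**Different protocol versions.** The SAP was written against Amendment 1, whereas the protocol in hand is Amendment 2, whose change list includes unspecified editorial edits. SAP 2.1 therefore cannot vouch for the current table. That is fair, but it leaves the protocol table's internal conflict untouched.

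**The prior and cut-off.** The tables give a decision for every count up to n = 15, so no site needs the threshold in order to act, and the SAP cites the mTPI-2 method paper. This stands: stating the rule is missing detail, separate from the wrong cell.

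**No practical effect.** Both codes lower the dose for the next cohort. Eleven evaluable participants exceeds the 6 to 9 planned at the MTD, a dose level review team looks at each cohort, Phase 2 will not start, and an amendment is a heavy instrument for a closing study. All of this stands and sets the rating. It does not make the cell right.

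**Conclusion.** The concern holds, as a minor consistency error. Protocol Table 12 and SAP Table 3 disagree at 6/11, and the protocol's D is the inconsistent entry. The 0.953 and 0.961 figures and the implied cut-off range assume a uniform prior. The finding that no single cut-off can yield DU at 5/9 and D at 6/11 held for every prior tried. Across the cohort sequences examined, the chance of reaching the cell is at most 0.4% at a true DLT rate of 0.4 and 0.6% at 0.5, or 0.6% and 0.9% if escalation signals at the top dose allow staying. The two entries differ only in whether the dose may be revisited, so no trial result is expected to change. The one open point is confirmation of the printed letter on the source PDF.

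**What to change.** Check the 6/11 cell on the source PDF. If it prints D, change protocol Table 12 at 6 DLTs in 11 patients to DU, to match SAP Table 3. If no further amendment is planned, a note to file, or a statement in the clinical study report of which table governed, would do the same job.

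It would also help to add one sentence to protocol 9.7 and one to SAP 5.1.2 giving the prior and the elimination cut-off. Elimination when P(p > 0.3) > 0.95 under Beta(1,1) fits every complete SAP row, but the sponsor should confirm that this is the rule that was used.

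The edit itself is one table cell and one sentence in each document. If it is made as a formal amendment, the review that goes with one is an added cost.

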## 10. SUPPORTING DOCUMENTATION AND OPERATIONAL CONSIDERATIONS

### 10.1. Appendix 1: Regulatory, Ethical, and Study Oversight Considerations

#### 10.1.1. Regulatory and Ethical Considerations

This study will be conducted in accordance with the protocol and with the following:

- Consensus ethical principles derived from international guidelines, including the Declaration of Helsinki and CIOMS International Ethical Guidelines;
- Applicable ICH GCP guidelines;
- Applicable laws and regulations, including applicable privacy laws.

The protocol, protocol amendments, ICD, SRSD(s), and other relevant documents (eg, advertisements) must be reviewed and approved by the sponsor, submitted to an IRB/EC by the investigator, and reviewed and approved by the IRB/EC before the study is initiated.

Any amendments to the protocol will require IRB/EC approval before implementation of changes made to the study design, except for changes necessary to eliminate an immediate hazard to study participants.

Protocols and any substantial amendments to the protocol will require health authority approval prior to initiation except for changes necessary to eliminate an immediate hazard to study participants.

The investigator will be responsible for the following:

- Providing written summaries of the status of the study to the IRB/EC annually or more frequently in accordance with the requirements, policies, and procedures established by the IRB/EC.
- Notifying the IRB/EC of SAEs or other significant safety findings as required by IRB/EC procedures.
- Providing oversight of the conduct of the study at the site and adherence to requirements of 21 CFR, ICH GCP guidelines, the IRB/EC, European regulation 536/2014 for clinical studies, European MDR 2017/745 for clinical device research, and all other applicable local regulations.

#### 10.1.1.1. Reporting of Safety Issues and Serious Breaches of the Protocol or ICH GCP

In the event of any prohibition or restriction imposed (ie, clinical hold) by an applicable regulatory authority in any area of the world, or if the investigator is aware of any new information that might influence the evaluation of the benefits and risks of the study intervention, Pfizer should be informed immediately.

In addition, the investigator will inform Pfizer immediately of any urgent safety measures taken by the investigator to protect the study participants against any immediate hazard, and of any serious breaches of this protocol or of the ICH GCP that the investigator becomes aware of.

#### **10.1.2. Financial Disclosure**

Investigators and sub-investigators will provide the sponsor with sufficient, accurate financial information as requested to allow the sponsor to submit complete and accurate financial certification or disclosure statements to the appropriate regulatory authorities. Investigators are responsible for providing information on financial interests during the course of the study and for 1 year after completion of the study.

#### **10.1.3. Informed Consent/Assent Process**

The investigator or the investigator's representative will explain the nature of the study, including the risks and benefits, to the participant or their legally authorized representative and answer all questions regarding the study. The participant or their legally authorized representative should be given sufficient time and opportunity to ask questions and to decide whether or not to participate in the trial.

Participants must be informed that their participation is voluntary. Participants or their legally authorized representative (if allowed by local regulations) will be required to sign a statement of informed consent that meets the requirements of 21 CFR 50, local regulations, ICH GCP guidelines, privacy and data protection requirements, where applicable, and the IRB/EC or study center.

The investigator must ensure that each study participant or their legally authorized representative is fully informed about the nature and objectives of the study, the sharing of data related to the study, and possible risks associated with participation, including the risks associated with the processing of the participant's personal data.

The participant or their legally authorized representative must be informed that their personal study-related data will be used by the sponsor in accordance with local data protection law. The level of disclosure must also be explained to the participant or their legally authorized representative.

The participant or their legally authorized representative must be informed that their medical records may be examined by Clinical Quality Assurance auditors or other authorized personnel appointed by the sponsor, by appropriate IRB/EC members, and by inspectors from regulatory authorities.

The investigator further must ensure that each study participant or their legally authorized representative is fully informed about his or her right to access and correct their personal data and to withdraw consent for the processing of his or her personal data.

The medical record must include a statement that written informed consent was obtained before the participant was enrolled in the study and the date on which the written consent was obtained. The authorized person obtaining the informed consent must also sign the ICD.

Participants or their legally authorized representative must be reconsented to the most current IRB/EC version of the IRB/EC-approved ICD(s) during their participation in the study as required per local regulations.

A copy of the ICD(s) must be provided to the participant or their legally authorized representative (if allowed by local regulations).

A participant who is rescreened is not required to sign another ICD if the rescreening occurs within 28 days from the previous ICD signature date.

#### **10.1.4. Data Protection**

All parties will comply with all applicable laws, including laws regarding the implementation of organizational and technical measures to ensure protection of participant data.

Participants' personal data will be stored at the study site in encrypted electronic and/or paper form and will be password-protected or secured in a locked room to ensure that only authorized study staff have access. The study site will implement appropriate technical and organizational measures to ensure that the personal data can be recovered in the event of disaster. In the event of a potential personal data breach, the study site will be responsible for determining whether a personal data breach has in fact occurred and, if so, providing breach notifications as required by law.

To protect the rights and freedoms of participants with regard to the processing of personal data, participants will be assigned a single, participant-specific numerical code. Any participant records or data sets that are transferred to the sponsor will contain the numerical code; participant names will not be transferred. All other identifiable data transferred to the sponsor will be identified by this single, participant-specific code. The study site will maintain a confidential list of participants who participated in the study, linking each participant's numerical code to their actual identity and medical record ID. In case of data transfer, the sponsor will protect the confidentiality of participants' personal data consistent with the clinical study agreement and applicable privacy laws.

Information technology systems used to collect, process, and store study-related data are secured by technical and organizational security measures designed to protect such data against accidental or unlawful loss, alteration, or unauthorized disclosure or access.

The sponsor maintains SOPs on how to respond in the event of unauthorized access, use, or disclosure of sponsor information or systems.

#### **10.1.5. Committees Structure**

This study will not use an E-DMC.

#### **10.1.6. Dissemination of Clinical Study Data**

Pfizer fulfills its commitment to publicly disclose clinical study results through posting the results of studies on [www.clinicaltrials.gov](http://www.clinicaltrials.gov) (ClinicalTrials.gov), the EudraCT/CTIS, and/or [www.pfizer.com](http://www.pfizer.com), and other public registries and websites in accordance with applicable local laws/regulations. In addition, Pfizer reports study results outside of the requirements of local laws/regulations pursuant to its SOPs.

In all cases, study results are reported by Pfizer in an objective, accurate, balanced, and complete manner and are reported regardless of the outcome of the study or the country in which the study was conducted.

[www.clinicaltrials.gov](http://www.clinicaltrials.gov)

Pfizer posts clinical trial results on [www.clinicaltrials.gov](http://www.clinicaltrials.gov) for Pfizer-sponsored interventional studies (conducted in patients) that evaluate the safety and/or efficacy of a product, regardless of the geographical location in which the study is conducted. These results are submitted for posting in accordance with the format and timelines set forth by US law.

EudraCT/CTIS

Pfizer posts clinical trial results on EudraCT/CTIS for Pfizer-sponsored interventional studies in accordance with the format and timelines set forth by EU requirements.

[www.pfizer.com](http://www.pfizer.com)

Pfizer posts CSR synopses and plain-language study results summaries on [www.pfizer.com](http://www.pfizer.com) for Pfizer-sponsored interventional studies at the same time the corresponding study results are posted to [www.clinicaltrials.gov](http://www.clinicaltrials.gov). CSR synopses will have personally identifiable information anonymized.

Documents within marketing applications

Pfizer complies with applicable local laws/regulations to publish clinical documents included in marketing applications. Clinical documents include summary documents and CSRs including the protocol and protocol amendments, sample CRFs, and SAPs. Clinical documents will have personally identifiable information anonymized.

Data sharing

Pfizer provides researchers secure access to participant-level data or full CSRs for the purposes of “bona-fide scientific research” that contributes to the scientific understanding of the disease, target, or compound class. Pfizer will make data from these trials available 18 months after study completion. Participant-level data will be anonymized in accordance with applicable privacy laws and regulations. CSRs will have personally identifiable information anonymized.

Data requests are considered from qualified researchers with the appropriate competencies to perform the proposed analyses. Research teams must include a biostatistician. Data will not be provided to applicants with significant conflicts of interest, including individuals requesting access for commercial/competitive or legal purposes.

